2.3.1 Risk assessment

No tissue targets or specific hazards to humans were identified in nonclinical general and reproductive toxicology studies.

Dupilumab has an extensive safety database. As of 28 September 2020, 10 773 participants had been enrolled into the development program for dupilumab and are included in the safety population. The estimated number of participants exposed to dupilumab in clinical studies was 9110 (356 in healthy volunteer studies, 4130 in AD studies, 3319 in asthma studies, 470 in CRSwNP studies, 226 in eosinophilic esophagitis studies, 176 in the grass/peanut allergy studies, 355 in the chronic obstructive pulmonary disease (COPD) studies, 36 in prurigo nodularis (PN) studies, and 42 in the chronic spontaneous urticaria (CSU) study).

Based on the sales figures and the World Health Organization defined daily dose of 21.4 mg/day, the cumulative postmarketing exposure to dupilumab could be estimated to be 249 341 patient years from 01 January 2017 through 30 September 2020.

Dupilumab was generally well tolerated in all populations tested in clinical development programs, consistent with a favorable benefit/risk profile. The adverse drug reactions (ADRs) identified to date for dupilumab include injection site reactions, conjunctivitis (including allergic and bacterial), oral herpes, herpes simplex, blepharitis, dry eye, eye pruritus, eosinophilia, pyrexia, headache, arthralgia, anaphylaxis, serum sickness-like reaction, and serum sickness. These ADRs were generally mild or moderate, transient, and manageable. These ADRs were not observed consistently in all indications. More significant serious allergic reactions were very rare. Importantly, no increased overall risk of serious infection was observed in participants treated with dupilumab.

Systemic hypersensitivity is established as an important identified risk with dupilumab. As protein therapeutics, all monoclonal antibodies are potentially immunogenic. Rare serious and systemic hypersensitivity reactions have been observed in the dupilumab program, including serum sickness or serum sickness-like reaction in the adult AD program and anaphylaxis related to dupilumab in the adult asthma clinical studies.

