8.2.7 Hypersensitivity monitoring

Allergic reaction is a potential risk associated with the administration of most therapeutic monoclonal antibody treatments.

Allergic reactions may be defined as allergic reaction-mediated signs and symptoms experienced by participants during or shortly after a pharmacologic or biologic agent is given. These reactions may present in a variety of ways, including dizziness, headache, anxiety, dyspnea, hypotension, tachycardia, pruritus, rash, urticaria/angioedema, flushing, nausea or vomiting, and joint pain with fever. Allergic reactions may begin within a few hours and persist up to 24 hours after dosing.

Refer to Appendix 12 ([Section 10.12](#)), which describes the clinical criteria for the diagnosis of anaphylaxis.

Participants should be monitored for at least 30 minutes after each study site IMP administration for any signs or symptoms of a hypersensitivity reaction. Any instance of allergic reaction should be reported as an AESI ([Section 8.3.6](#)). Any anaphylactic reactions or acute allergic reactions that require immediate treatment will be an AESI with immediate reporting (within 24 hours), and study medication must be permanently discontinued. Trained personnel and medications should be available to treat anaphylaxis or any severe allergic reaction if it occurs. Furthermore, the study participants will be advised, when the IMP is administered at home, to self-monitor for potential signs and symptoms that may suggest a hypersensitivity reaction for at least 30 minutes after administration.

Anaphylactic reactions or systemic allergic reactions that are related to IMP and require treatment must be reported as an AESI (within 24 hours; for further details, see AESI definition in [Section 8.3.6](#)), and study medication must be permanently discontinued.

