8.3.6 Adverse event of special interest

An AESI is an AE (serious or nonserious) of scientific and medical concern specific to the Sponsor's product or program, for which ongoing monitoring and immediate notification by the Investigator to the Sponsor are required. Such events may require further investigation in order to characterize and understand them. Adverse events of special interest may be added, modified, or removed during a study by protocol amendment.

For these AESIs, the Sponsor will be informed immediately (ie, within 24 hours), per the SAE notification described in [Section 10.3.4](#), even if it does not fulfill a seriousness criterion.

Adverse event of special interests for this study include the following:

- Anaphylactic or systemic allergic reactions that are related to IMP and that require treatment (refer to Appendix 12 [[Section 10.12](#)] for the definition of anaphylaxis)
 - Severe injection site reactions that last longer than 24 hours
 - Conjunctivitis, blepharitis, or keratitis
 - Serum sickness or serum sickness-like reaction
 - Clinically symptomatic eosinophilia (or eosinophilia associated with clinical symptoms)
 - Any infection meeting at least 1 of the following criteria:
 - Any SAE of serious infection
 - Requires parenteral (intravenous, intramuscular, SC) antimicrobial therapy
 - Requires oral antimicrobial therapy for longer than 2 weeks
 - Is a parasitic infection
 - Is an opportunistic infection (refer to Appendix 9 [[Section 10.9](#)])
- Note:** Antimicrobial therapy refers to antibiotic, antiviral, and antifungal agents.
- Significant elevation of alanine aminotransferase (ALT)
 - $ALT > 5 \times ULN$ in participants with baseline $ALT \leq 2 \times ULN$
 - or
 - $ALT > 8 \times ULN$ if baseline $ALT > 2 \times ULN$
 - Pregnancy of a female participant as well as pregnancy occurring in a female partner of a male participant entered in a study with IMP
 - Pregnancy occurring in a female participant entered in the clinical study or in a female partner of a male participant entered in the clinical study. It will be qualified as an SAE only if it fulfills one of the seriousness criteria (see Appendix 3 [[Section 10.3](#)]).
 - In the event of pregnancy in a female participant, IMP should be discontinued.
 - Follow-up of the pregnancy in a female participant or in a female partner of a male participant is mandatory until the outcome has been determined (See Appendix 4 [[Section 10.4](#)]).

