**Table 9 - Selections for AESIs and other AEs of interest**

AESIs [and other AEs of interest]	Selection
AESI	
Anaphylactic reactions	Anaphylactic reaction algorithmic approach (Introductory Guide for Standardised MedDRA Queries (SMQs)): includes anaphylactic reaction narrow SMQ (2000021) terms and programmatic identification of cases based on occurrence of at least two preferred terms meeting the algorithm criteria occurring within 24 hours of each other. The latter cases identified using the algorithm will undergo blinded medical review taking into account the timing of events relative to each other and to IMP administration for final determination of an anaphylactic reaction or not.
Systemic hypersensitivity reactions	SMQ [20000214] hypersensitivity narrow search and [AE corrective treatment/therapy='Y' or Action taken with IMP='Drug withdrawn' or Action taken with IMP='Drug interrupted'] followed by blinded medical review (documented process) for selection of relevant systemic hypersensitivity events
Helminthic infections	CMQ10544 based on HLT as "Helminthic disorder"
Any severe type of conjunctivitis	CMQ10498 based on PTs (See Section 5.6)a and "Severe" ticked in Adverse Events eCRF page
Any severe type of blepharitis.	CMQ10497 based on HLT as "Lid, lash and lacrimal infections, irritations and inflammations" and "Severe" ticked in Adverse Events eCRF page
Keratitis	CMQ10642 based on the following PTs [keratitis, allergic keratitis, ulcerative keratitis, atopic keratoconjunctivitis, herpes ophthalmic, ophthalmic herpes simplex, corneal infection]a
Clinically symptomatic eosinophilia (or eosinophilia associated with clinical symptoms)b	CMQ10641 based on HLT = Eosinophilic disorders or PT=Eosinophil count increased
Significant ALT elevation	ALT >5 × the ULN in participants with baseline ALT ≤2 × ULN for age; OR ALT >8 × ULN for age if baseline ALT >2 × ULN for age
Pregnancy of a female subject entered in a study as well as pregnancy occurring in a female partner of a male subject entered in a study with IMP/NIMP	"Pregnancy" or "Partner Pregnancy" checked on thePregnancy eCRF page as reported by the investigator
Symptomatic overdose (serious or nonserious) with IMP/NIMP.	Symptomatic Overdose is answered Yes, with Overdose of IMP answered Yes on AE eCRF.
Other selected AE Grouping	

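### The AESI block of SAP Table 9 does not match the AESI list in protocol 8.3.6, and the SAP does not say which rows feed the any-AESI line (minor)

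*SAP*

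**What the plan says.** Protocol 8.3.6 lists "Conjunctivitis, blepharitis, or keratitis" as AESIs with no severity condition. It also lists "Serum sickness or serum sickness-like reaction", severe injection site reactions lasting more than 24 hours, and any infection that meets at least one of five criteria. Two of the five are "Requires parenteral (intravenous, intramuscular, SC) antimicrobial therapy" and "Requires oral antimicrobial therapy for longer than 2 weeks"; the others are serious, parasitic and opportunistic infection. The same section says the list is changed by protocol amendment. Protocol 9.3.5 leaves AESI definitions and the method of identifying them to the SAP, and 9.3.5.1 promises an incidence table for all treatment-emergent AESIs.

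SAP 4.7.2 puts an any-AESI line in the TEAE overview and selects AESIs through Table 9, which has two blocks. The AESI block contains "Any severe type of conjunctivitis" and "Any severe type of blepharitis", each requiring the severe box to be ticked on the adverse event page. Its only infection row is helminthic infections, and it has no injection site row. The second block, Other selected AE Grouping, holds the injection site rows, severe or serious infection, parasitic and opportunistic infection, and three wider conjunctivitis groupings.

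**The concern.** A programmer who follows the AESI block exactly will leave a mild or moderate conjunctivitis or blepharitis out of the eye AESI rows, although the site had to report it as an AESI within 24 hours under 8.3.6. The same applies to several kinds of infection and to severe, prolonged injection site reactions. If the any-AESI line is built from that block, it may undercount protocol-defined AESIs and fail to reconcile with the site reports.

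The severity condition is not a trivial filter for this product. Protocol 2.3.1 names conjunctivitis and blepharitis among the identified adverse reactions and says of the whole group: "These ADRs were generally mild or moderate, transient, and manageable".

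Nothing in the documents declares the difference. The protocol amendment history (Appendix 14) is marked not applicable. The SAP version history reports no major change from the protocol. SAP Appendix 2 lists only two changes: the treatment-emergent period and the definition of rescue.

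**Working it through.** No figure in the plan is at issue, so the check sets the 8.3.6 criteria for these four groups beside the two blocks of Table 9.

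| Protocol 8.3.6 criterion | AESI block | Other block |
|---|---|---|
| Conjunctivitis | only if ticked severe | three groupings, any severity |
| Blepharitis | only if ticked severe | one term in the broad conjunctivitis row |
| Keratitis | term list, no severity limit | no separate row |
| Severe injection site reaction over 24 h | no row | row, wider: adds serious reactions |
| Serum sickness | no named row | no named row |
| Serious infection | no row | row, wider: adds severe infections |
| Parenteral antimicrobial needed | no row | no row |
| Oral antimicrobial over 2 weeks | no row | no row |
| Parasitic infection | helminthic only | row |
| Opportunistic infection | no row | row |

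- **Tally.** 3 eye + 1 injection site + 1 serum sickness + 5 infection = 10 criteria. In the AESI block, 1 is covered fully (keratitis), 3 partly (conjunctivitis, blepharitis, parasitic), and 10 − 1 − 3 = 6 have no row of their own. Of those 6, 3 have a row in the Other block (injection site, serious infection, opportunistic). The other 3 have no named row in either block (serum sickness and the two antimicrobial criteria).
- **Infection form.** The parasitic and opportunistic rows are read from an eCRF form whose title calls the infection an AESI, yet both rows sit outside the AESI block.
- **Serum sickness.** It can enter the systemic hypersensitivity row only if three things hold: the narrow query contains the term; the event was treated, or IMP was withdrawn or interrupted; and medical review keeps it. The documents do not show what the query contains.
- **Any-AESI line from the AESI block alone.** It misses non-severe conjunctivitis and blepharitis, and the infection and injection site criteria without a row.
- **Any-AESI line from all of Table 9.** It still lacks the two antimicrobial criteria. It also adds events that 8.3.6 does not list, such as any injection site reaction or dry eye. Neither construction reproduces 8.3.6, and the SAP does not say which is meant, or whether an investigator flag is used.
- **Conjunctivitis terms.** SAP Section 5.6 lists 28 preferred terms. The narrow, broad and FDA groupings together contain 6 of them: conjunctivitis; its allergic, bacterial and viral forms; conjunctival hyperaemia; and giant papillary conjunctivitis. That leaves 28 − 6 = 22 that a non-severe event could carry without entering any conjunctivitis row. Four of the 22 are neonatal terms with no relevance to adults, and one is Seasonal allergy, whose place in the list is itself doubtful.

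**The case against.** The best defence is delegation. Protocol 9.3.5 hands AESI definitions to the SAP, and 9.3.5.1 allows a preferred term or a prespecified grouping. The amendment sentence in 8.3.6 could be read as governing site notification only. That makes a deliberate analysis definition possible. It does not explain why the SAP uses the same label for a different set of events without saying so.

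A second defence is that this is largely a matter of which subheading a row sits under. Much of it is. SAP 4.7.2 gives counts for every event of interest, and the Other rows for injection site reactions and infections are wider than 8.3.6. Some stronger inferences therefore fail:

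- **Non-severe blepharitis is lost, or visible only in the broad conjunctivitis row.** SAP Table 8 tabulates all TEAEs by high-level term and preferred term, and again by maximal intensity. The blepharitis selection is itself a high-level term, so any-severity counts exist there.
- **Serum sickness is simply omitted.** Protocol 2.3.1 places it among systemic hypersensitivity reactions, and Table 9 has a row for those. Capture is uncertain; omission is not shown.
- **A likely number of missed events.** The documents give no eye event rates for this population, and 2.3.1 adds that the reactions were not seen consistently across indications. No probability can be supported.
- **Eosinophilia and allergic reactions belong to the same narrowing.** Table 9 footnote b openly counts all eosinophilia, which is wider than 8.3.6. For allergic reactions the conflict lies within the protocol: 8.2.7 says "Any instance of allergic reaction should be reported as an AESI", while 8.3.6 requires relation to IMP and a need for treatment.

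**Conclusion.** The mismatch between Table 9 and protocol 8.3.6 is real and can be read directly from the text. In the eye rows the shortfall follows from the stated selection rule. In the any-AESI line it depends on how that line is built, which the SAP leaves open. The clearest gap is an infection that is neither severe, serious, parasitic nor opportunistic and qualifies only through its antimicrobial treatment: no row in Table 9 selects it.

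The size is small. AESI incidence is not a listed endpoint, no hypothesis is tested, and the events remain visible in the Other rows or the TEAE tables. As a scale only, if all of the approximately 25 planned participants are in the safety population, each participant left out moves an AESI percentage by 1/25 = 4 points. How many would be left out, if any, cannot be said. The point is minor. It does not support a claim that safety events would go unreported or that any efficacy conclusion is affected.

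**What to change.** Build the AESI block and the any-AESI line from the 8.3.6 criteria, and name the rows that feed the line.

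- Remove the severe condition for conjunctivitis and blepharitis, and keep the severe-only rows as subsets. Check the Section 5.6 term list first, for example Seasonal allergy.
- Move the injection site and the serious, parasitic and opportunistic infection rows into the AESI block, using the 8.3.6 criteria in place of the wider ones now in the Other block.
- Add a serum sickness row, and rows for the two antimicrobial criteria where the eCRF captures them.
- Record any intended departure, with its reason, in SAP Appendix 2.

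Separately, protocol 8.2.7 and 8.3.6 must be reconciled on which allergic reactions are AESIs, and the SAP row aligned with the outcome.

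The SAP part costs a table edit and some programming. The documents do not show whether the infection form records antimicrobial route and duration, so that needs checking first. Reconciling 8.2.7 with 8.3.6 means changing protocol text, which is a larger step and need not hold up the SAP edit.

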### 4.7.3 Additional safety assessments

#### 4.7.3.1 Laboratory variables, vital signs and electrocardiograms (ECGs)

The following laboratory variables and vital signs will be converted into standard international units and analyzed.

- Hematology:
  - Red blood cells and platelets and coagulation: [hemoglobin, hematocrit, red blood cell count, platelet count
  - White blood cells: white blood cell count, neutrophils, lymphocytes, monocytes, basophils, eosinophils
- Clinical chemistry:
  - Metabolism: glucose, total cholesterol, total protein, albumin, creatine phosphokinase
  - Electrolytes: sodium, potassium, chloride
  - Renal function: creatinine, blood urea nitrogen, uric acid.  
Creatinine clearance will be derived with the equation of Cockcroft and Gault using weight assessed at the same visit as creatinine. eGFR will be derived using the Modification of the Diet in Renal Disease (MDRD) equation.
  - Liver function: alanine aminotransferase, aspartate aminotransferase, alkaline phosphatase, lactate dehydrogenase, total bilirubin
  - Pregnancy test: Serum and urine  $\beta$ -human chorionic gonadotropin (all childbearing potential female participants)
- Urinalysis:

- Urinalysis for quantitative analysis: pH, specific gravity, glucose, protein, blood, ketones, urobilinogen, nitrite by dipstick
- Vital signs:
  - pulse rate, systolic and diastolic blood pressure, weight, respiratory rate, temperature

ECG data are used for screening purposes only.

Data below the lower limit of quantitation/detection limit (LLOQ) will be replaced by half of the LLOQ, data above the upper limit of quantification will be replaced by ULOQ value.

Grading (LLN, ULN) will be derived using local laboratory normal ranges.

### **Quantitative analyses**

For all laboratory variables and vital signs above, descriptive statistics for results and changes from baseline will be provided for each planned visit during the on-treatment period. These analyses will be performed using local measurements, converted into SI units for laboratory variables.

### **Analyses according to PCSA**

Potentially clinically significant abnormality (PCSA) analyses will be performed based on the PCSA list currently in effect at Sanofi at the time of the database lock. Parameters with no PCSA criteria defined, similar analyses will be done using the local normal ranges, if applicable.

Analyses according to PCSA will be performed based on the worst value during the treatment-emergent period, using all measurements.

For laboratory variables and vital signs above, the incidence of participants with at least one PCSA during the treatment-emergent period will be summarized regardless of the baseline level and according to the following baseline status categories:

- Normal/missing
- Abnormal according to PCSA criterion or criteria

### ***Additional analyses for drug-induced liver injury(if applicable)***

The following additional analyses will be performed for drug-induced liver injury:

- A graph of the distribution of peak values of ALT versus peak values of total bilirubin during the treatment-emergent period will be provided.

## **4.8 OTHER ANALYSES**

No other analyses are planned.

#### **4.9 INTERIM ANALYSES**

No interim analysis is planned.

## 5 SUPPORTING DOCUMENTATION

### 5.1 APPENDIX 1 LIST OF ABBREVIATIONS

AE:	adverse event
AESIs:	adverse events of special interest
CI:	confidence interval, confidence interval
CRSwNP:	chronic rhinosinusitis with nasal polyps
CT:	computerized tomography
HGLT:	high level group term, high level group term, high level group term, high level group term
HLT:	high level term
INCS:	intranasal corticosteroid
ITT:	intent-to-treat
LLT:	lower-level term
LMK:	Lund Mackay
MCMC:	Markov Chain Monte Carlo
MedDRA:	Medical Dictionary for Regulatory Activities
mITT:	modified intent-to-treat
NE:	nasal endoscopy
NPS:	nasal polyp score
PCSA:	potentially clinically significant abnormality
PP:	per protocol
PPE:	per protocol extension
PT:	preferred term
q2w:	every 2 weeks
q4w:	every 4 weeks
SAF:	safety population
SAFE:	safety population for extension
SAP:	statistical analysis plan
SCS:	systemic corticosteroid
SOC:	system organ class
TEAE:	treatment-emergent adverse event
WHO-DD:	World Health Organization-Drug Dictionary
WOCF:	worst observation carried forward

### 5.2 APPENDIX 2 CHANGES TO PROTOCOL-PLANNED ANALYSES

Protocol Version	Approval Date	Changes	Rationale
1	11-May-2021	4.1 GENERAL CONSIDERATIONS	This is to prevent the case that patient discontinues treatment very

Protocol Version	Approval Date	Changes	Rationale
		
Observation period
 
 
The treatment-emergent period is defined as the period from the first IMP administration to the last visit in the study or the date of treatment discontinuation if discontinued from the study, whichever is earlier.
 
	
early, but have a EOS conducted, for example, 24 weeks after the last IMP.

		
4.1 GENERAL CONSIDERATIONS
 
Rescue
 
Participants who have undergone surgery or received SCS for any reasons, <del>and/or received selected prohibited medications</del> are considered rescued. NP surgery and SCS use will be determined by the corresponding eCRF pages, <del>while selected prohibited medications will be determined based on corresponding WHODD code in EFC14280.</del>
 
The date of rescue will be the earliest date of having undergone surgery or received SCS for any reason, <del>and/or received selected prohibited medications.</del>
 
And delete "selected prohibited medications" in the sections related to changes to the above definitions.
	
For the purpose of consistency with EFC14280, it focus the following data handling.
 
 
only surgery for NP or receive SCS triggers non-responder imputation
 
rescue treatment define as undergone surgery or received SCS
 

### 5.3 APPENDIX 3 DEMOGRAPHICS AND BASELINE CHARACTERISTICS, PRIOR OR CONCOMITANT MEDICATIONS

#### 5.3.1 Protocol deviations

Critical and major protocol deviations (automatic or manual), including drug dispensing irregularities, will be summarized in the Enrolled analysis population. Protocol deviations due to the COVID-19 pandemic will be categorized as such.

